3.2 Screening and Enrollment

Caregivers will be screened for eligibility Monday through Friday from 7 am to 6 pm. The PI or trained research assistant(s) will review currently admitted patients on the general hospital medicine teams who meet eligibility criteria and contact the attending physician to inquire about discharge status and request permission to approach the caregiver. For patients nearing discharge, caregivers will be approached to discuss the study and confirm eligibility (see Interest in Participation Script). An eligibility script will be used to standardize this process (see included document) Patient-level randomization will occur at the time of enrollment. Allocation to intervention or usual care will be done by block randomization and will be assigned when individuals are determined to be eligible based on the eligibility script. Due to the nature of the intervention, it will not be possible to blind study staff or caregivers to the assigned study arm (intervention or usual care).

At the time of enrollment (i.e., either the day prior to discharge, if possible, or the day of discharge), caregivers in both groups will complete a demographics questionnaire via a secure web platform called REDCap (Research Electronic Data Capture).²⁶ Questions will include patient (child) age, sex, race/ethnicity, whether they were receiving any liquid medication prior to admission, number of previous hospitalizations, and number of previous daily medications. Demographic questions about caregivers will include age, gender, race/ethnicity, education level, caregiver relationship to patient, marital status of caregiver, education level of caregiver, employment status, difficulties paying bills (proxy for financial stress), country of origin, and preferred language. The following information will be extracted from the electronic health record: child discharge diagnosis, medication(s) name, number, frequency, dose and duration of discharge medication(s), patient insurance status, and number of chronic conditions.²⁷ Caregiver health literacy will be measured using the Newest Vital Sign (see included document).²⁸ The Newest Vital Sign has been translated into Spanish by the creators. See Figure 1 for study flow.

[figure not shown]
Figure 1. Aim 2 Study Flow

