3.5 Data Analysis and Sample Size

Data analysis: Baseline characteristics of the intervention and control groups will be compared using *t* tests and χ^2 tests or Fisher exact tests, as appropriate. Wilcoxon rank-sum tests will be used if the data does not appear to be normally distributed. These tests will be performed to also compare those who did and did not complete the follow-up assessment.

Randomization will be done using block permutation at the time of enrollment. Study staff enrolling caregivers will not be blinded to group allocation. Caregivers will not explicitly be told what group they have been assigned. Study staff will be blinded to group allocation when assessing the dose in the syringe in the picture submitted during follow-up in order to determine the primary outcome of observed dosing accuracy. Two independent study staff will assess the picture to determine the dose. Any disagreement will be adjudicated by the study PI.

The primary outcome will be the percent difference in the observed dose measured as the difference in millimeters (mL) between the dose of medication in the caregiver submitted picture during follow-up assessment compared to the prescribed dose in the electronic health record divided by the prescribed dose. For example, if the observed dose in the caregiver submitted picture was 4.5 mL and the prescribed dose in the electronic health record was 3 mL then this would be a 50% overdosing error. The observed dosing percent difference will be compared between the intervention and control groups as medians with interquartile ranges.

Last Revision: 4/21/2022

Table 4. Demographics of potentially eligible children, July 2018-June 2019 (N = 1,742)

Characteristic	N (%)
Age (y)	
0 to < 6 months	940 (54)
6 mos to <1yrs	183 (11)
12 mos to < 2 yrs	288(16)
2yrs to < 3yrs	205 (12)
3yrs to < 4 yrs	125 (7)
Sex	
Male	958 (55)
Female	784 (45)
Race/Ethnicity	
Non-Hispanic white	1098 (63)
Non-Hispanic black	244 (14)
Hispanic	296 (17)
Other	104 (6)

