If we detect covariate imbalance in the two groups, we will use propensity score weighting and a multivariable linear regression model to conduct an adjusted analysis. Proposed covariates to include in the model are: caregiver health literacy, caregiver age, caregiver gender, caregiver race/ethnicity, and caregiver primary language. These covariates are likely to have the biggest impact on the primary outcome. The other covariates includes caregiver country of origin, socioeconomic status (i.e., binary outcome of do you have difficulty paying bills), employment status, education status, and marital status. Patient level covariates include child age, gender race/ethnicity, medical complexity, number of previous medications and previous hospitalizations in the last year and insurance type.

We will display our findings for the continuous outcome of observed medication dosing error using either box plots or violin plots for the intervention and control groups.

Given that prior literature in this area has examined medication dose error as a dichotomous variable using +/- 20% from the prescribed dose (this was felt to be a clinically meaningful dosing error), we will also examine and display our primary outcome in this way to allow for comparison to other studies. We will report relative risk reduction, absolute risk reduction and number needed to treat along with 95% confidence intervals for the primary outcome of both observed dosing accuracy and reported dosing accuracy.

Sample Size: Sample size estimates are based on the outcome of medication dosing accuracy. Using a conservative dosing error prevalence of 30% in the control arm,^{2,4-6,15} and an expected dosing error prevalence of 10% in the intervention arm, we will need to enroll 72 subjects in each arm of the study to reject the null hypothesis that the dosing error prevalence in the control and intervention arms are equal with 80% power (2-sided alpha of 0.05). Accounting for 25-30% loss to follow-up, we plan to enroll a total of 200 subjects. From July 2018-June 2019, the pediatric hospital medicine service at Vanderbilt discharged 1,742 children <4 years of age, at least 50% of whom were discharged home on 1 or more medications (approximately 75 children per month), ensuring ample opportunities to achieve our required sample size (see Table 4).

3.6 Potential Limitations and Alternative Approaches for Aim 1

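### The adjusted analysis should not depend on detecting baseline imbalance: fix it in advance on the five covariates the plan already names, and extend it to the within-20% endpoint

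*Combined protocol and SAP*

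**What the plan says.** All analysis text is in Section 3.5 of the combined protocol and SAP.

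- **Baseline comparison.** "Baseline characteristics of the intervention and control groups will be compared using" t tests, chi-square or Fisher tests, or rank-sum tests where normality is doubtful. No cut-off for imbalance is given.
- **Continuous primary outcome.** "The observed dosing percent difference will be compared between the intervention and control groups as medians with interquartile ranges".
- **Adjustment.** "If we detect covariate imbalance in the two groups, we will use propensity score weighting and a multivariable linear regression model". Five caregiver covariates are proposed for the model, with a reason: "These covariates are likely to have the biggest impact on the primary outcome".
- **Further covariates.** "The other covariates includes caregiver country of origin, socioeconomic status", then employment, education and marital status (five caregiver items in all) and seven child-level items. Whether these 12 can trigger adjustment or enter the model is not said.
- **Within-20% endpoint.** "We will report relative risk reduction, absolute risk reduction and number needed to treat along with 95% confidence intervals". No adjusted outcome model is named for it, and it is not said whether the propensity weighting covers it.
- **Sample size.** "Sample size estimates are based on the outcome of medication dosing accuracy", with error prevalences of 30% and 10%.

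On data collection, Section 3.2 says that "caregivers in both groups will complete a demographics questionnaire via a secure web platform called REDCap". That questionnaire covers caregiver age, gender, race/ethnicity and preferred language. The same paragraph adds health literacy, measured with the Newest Vital Sign.

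**The concern.** Randomisation makes baseline differences among all randomised caregivers a matter of chance, so a test of those differences says nothing about which covariates are worth adjusting for. What matters is whether a covariate predicts the outcome. The plan has already made that judgement for five covariates, and then does not act on it unless a chance difference appears. In most trials run under such a rule the prognostic information would be collected and left unused.

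Two gaps follow from the same passage. The plan does not say whether the adjusted or the unadjusted result leads when both exist. And the only adjusted outcome model it names is linear, although the sample size rests on a binary endpoint. At stake are some precision and a small amount of freedom in choosing the result to report. The validity of the trial is not at stake.

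**Working it through.** **1. The plan's own figure.** Two-proportion formula, p1 = 0.30, p2 = 0.10, mean 0.20, difference 0.20, two-sided alpha 0.05, power 80%:

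n = [1.96·√(2·0.20·0.80) + 0.8416·√(0.30·0.70 + 0.10·0.90)]² / 0.20² = (1.1087 + 0.4610)² / 0.04 = 61.6.

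With continuity correction: n = (61.6/4)·[1 + √(1 + 4/(61.6·0.20))]² = 15.4 × 4.627 = 71.25, so 72 per arm. The plan's figure is reproduced. Enrolling 200 fits the stated 25–30% loss: 144/(1 − 0.28) = 200. The calculation is an unadjusted comparison of error rates, so it does not rely on adjustment.

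**2. How often chance alone would trigger adjustment.** Assumption, not in the documents: imbalance means any baseline p < 0.05, with independent covariates.

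- Five named covariates: 1 − 0.95⁵ = 22.6%.
- All 17 listed (5 + 5 + 7): 1 − 0.95¹⁷ = 58.2%. With a common correlation of 0.3 or 0.5 (assumed) this falls to 49% or 38%.

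**3. Precision.** Simulation with 72 per arm and 40,000 trials per setting: five covariates sharing an assumed R² equally, 12 further covariates with no effect. The ratio compares the SD of the estimate when adjusting for the five only if triggered with the SD when always adjusting for them.

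| Assumed R² | Five can trigger | 17 can trigger |
|---|---|---|
| 0 | 0.990 | 0.995 |
| 0.1 | 1.020 | 1.010 |
| 0.2 | 1.058 | 1.031 |
| 0.3 | 1.105 | 1.058 |

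Smaller repeat simulations gave 1.09 to 1.10 for the five-covariate trigger at R² = 0.3, so the loss there is about 10%. The documents give no R².

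**4. Type I error (nominal 5%), same setting.**

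- Trigger followed strictly: 4.4–4.9% (five) and 4.6–5.0% (17).
- Better of the unadjusted and five-covariate results, chosen only when triggered: 5.1–5.7% (five) and 5.3–6.6% (17) in 6,000 trials per setting; 5.4–5.6% and 5.7–6.4% in 20,000.
- Adding a 17-covariate model as a third option when triggered: 6.7–7.3% at R² of 0.1 and 0.3.

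**5. What routine adjustment would do to power.** Illustrations at 30% vs 10% errors:

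- Linear model, every error taken as +50% and other doses with SD 5% (assumed): 82% adjusted vs 84% unadjusted if the covariates are not prognostic; 85 vs 83% and 88 vs 80% if they remove about 11% and 23% of the variance.
- Adjusted risk difference for the within-20% endpoint: 86 vs 88%, 85 vs 85% and 92 vs 85% at variance reductions of about 0, 4 and 21%.
- Weighting on the same five covariates gave nearly the same SD as a binary-outcome model in the strongest setting (0.058 vs 0.057), so either route serves.

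**6. Limits on the model.** Expected errors among 144 completers: 0.30 × 72 + 0.10 × 72 = 21.6 + 7.2 = 28.8. With arm plus five single-term covariates that is 28.8/6 = 4.8 per parameter.

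**7. The signed mean.** The linear model compares mean signed percent differences. If errors split 80/20 between +50% and −50%, its power is 35% adjusted and 37% unadjusted; with an even split it is about 5%. Adjustment does not cure this.

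**The case against.** The plan can be defended on several counts.

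- **The covariates are named.** A reader might infer that there is no covariate set at all. The text does not support that: five are proposed for the model, with a reason, and the other 12 are listed separately. Only the role of those 12 is open.
- **The unadjusted result reads as the lead.** The medians and the risk measures are unconditional, and the adjusted analysis happens only sometimes. That is the natural reading, and a missing sentence to confirm it is a small omission.
- **Error control.** A reader might infer that the conditional rule inflates type I error. Followed strictly, it does not. Simulated rates of 5.8–7.8% can be obtained by letting the analyst take the better of two results in every trial, but the plan allows adjustment only when imbalance is found, so that scenario sets aside the plan's own condition.
- **The gain is conditional.** For the within-20% endpoint, power rises clearly only at about 21% variance reduction, and nothing in the documents says the covariates are that prognostic.
- **Imbalance among completers need not be chance.** With 25–30% loss expected, the analysed arms may differ for reasons other than randomisation. This stands, and is a reason to keep the other 12 covariates available.

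What remains is that the trigger ignores the plan's own statement of which covariates matter, and that the endpoint behind the sample size has no stated adjusted analysis.

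**Conclusion.** The concern holds as a matter of efficiency and completeness. A rule that adjusts for the five named covariates whatever the baseline table shows is better than one that waits for a detected imbalance. Under independent 5% tests the trigger would fire in about 23% of trials on the five covariates, at a cost of about 2 to 10% in the SD of the estimate for R² of 0.1 to 0.3. At R² = 0 the trigger costs nothing and is about 1% more precise. The test rule, the independence and the R² values are all assumptions.

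The bias argument is weak: no inflation if the trigger is followed, and about 5 to 6.6% if the better of two results is chosen when it fires. A reader might also infer that an adjusted linear model should replace the medians. The documents do not support that, since it targets a different quantity, in which over- and under-doses can cancel. The change is worth making, but the trial's conclusions do not depend on it.

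**What to change.** Delete the imbalance condition in Section 3.5 and state the following:

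1. An analysis adjusted for caregiver health literacy, age, gender, race/ethnicity and primary language is done regardless of baseline balance, with the unadjusted result reported beside it. Say that the language variable is the preferred-language item in Section 3.2, if so.
2. The lead result (adjusted or unadjusted) is named in writing before the arms are compared.
3. For the within-20% endpoint, a binary-outcome model, or weighting on the same five covariates, gives adjusted risks in each arm, so that ARR, RRR and NNT are reported both adjusted and unadjusted. No particular estimator needs to be prescribed.
4. For the continuous outcome, the medians and IQRs stay. The linear model is described as estimating a difference in signed means, in which over- and under-doses can cancel, and does not displace them.
5. The other 12 covariates neither trigger nor enter this model. They may be used in a labelled sensitivity analysis, for example for loss to follow-up.

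**Cost.** SAP wording and a little analysis time; no new data. Enrolment was planned from July 2021 for 12 months and the text was last revised on 4/21/2022, so the change should be dated before any comparison of the arms. With about 29 expected errors the model must stay small, one term per covariate, which loses detail on race/ethnicity. If the covariates turn out not to be prognostic, about 2 points of power are lost.

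### The covariate lists contain no feature of the medicine, although prescribed volume is the denominator of the primary outcome and is already collected; adjusting for it may gain precision at almost no cost

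*Combined protocol and SAP*

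**What the plan says.** All of the covariate plan is in section 3.5 (Data Analysis and Sample Size).

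- **First-line covariates:** "caregiver health literacy, caregiver age, caregiver gender, caregiver race/ethnicity, and caregiver primary language". Of these the plan says "These covariates are likely to have the biggest impact on the primary outcome".
- **Other caregiver covariates:** "The other covariates includes caregiver country of origin, socioeconomic status", followed by employment, education and marital status.
- **Patient covariates:** "Patient level covariates include child age, gender race/ethnicity, medical complexity, number of previous medications and previous hospitalizations in the last year and insurance type".
- **When they are used:** only in an adjusted analysis (propensity weighting and linear regression) that is triggered by a detected imbalance. The primary comparison itself is unadjusted, as medians with interquartile ranges.
- **Primary outcome:** the mL difference "compared to the prescribed dose in the electronic health record divided by the prescribed dose". A second version classes a dose as accurate if it is within 20% of the prescribed dose.

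Section 3.2 (Screening and Enrollment) lists what is extracted from the health record, including "medication(s) name, number, frequency, dose and duration of discharge medication(s". The enrolment questionnaire also asks "whether they were receiving any liquid medication prior to admission".

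Section 3.3 says that the syringe given to families is the smallest that can hold the dose. This stands under the intervention. The size of the sealed-envelope syringe for usual care is not stated.

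**The concern.** The outcome is an error in mL "divided by the prescribed dose". The same slip of the plunger is therefore a large percent error on a small volume and a trivial one on a large volume. A variable that enters the outcome by definition is a natural candidate for adjustment, and here it is missing from every list while ten caregiver traits are named.

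Two things could be lost. One is precision: if volume explains part of the variation in percent error, an analysis that ignores it has a larger standard error than it needs. The other is protection against chance. Adjustment is triggered by imbalance and draws on named covariates, so an imbalance in volume has no stated route into the model.

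**Working it through.** **1. The plan's own figure.** Inputs from section 3.5: 30% v 10% error, 80% power, two-sided alpha 0.05.

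- Uncorrected: n = [1.96·√(2·0.2·0.8) + 0.842·√(0.3·0.7 + 0.1·0.9)]² / 0.2² = 61.6, so 62 per arm.
- With continuity correction: (61.6/4)·[1 + √(1 + 4/(61.6·0.2))]² = 71.3, so 72 per arm.

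The stated 72 reproduces. It is an unadjusted comparison of two proportions, so the choice of covariates does not alter it.

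**2. What the definition implies.** Percent error = 100 × mL error / prescribed mL. For a 0.2 mL error:

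| Prescribed mL | 0.5 | 1 | 3 | 5 | 10 |
|---|---|---|---|---|---|
| Percent error | 40 | 20 | 6.7 | 4 | 2 |

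**3. The 20% threshold under constant mL error.** Assume a zero-centred normal mL error with SD 0.2 at every volume. Then P(error > 20%) = 2·[1 − Φ(0.2·V/0.2)], which is 62% at 0.5 mL, 32% at 1 mL, 5% at 2 mL and about 0% at 5 mL.

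**4. Share of outcome variance explained by volume.** Assumed: lognormal volumes, median 3 mL, log-SD 0.5, 0.7 or 0.9, limited to 0.5–15 mL. The ranges run over the three log-SDs.

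| Error model | R², signed percent error | R², absolute percent error |
|---|---|---|
| Constant mL error, SD 0.3, centred on zero | about 0 | 0.17–0.19 on V; 0.25–0.35 on log V; 0.28–0.44 on 1/V |
| The same with a +0.2 mL bias | 0.06–0.07 on V; 0.09–0.17 on 1/V | 0.18–0.19 on V; 0.26–0.36 on log V; 0.29–0.46 on 1/V |
| Error proportional to dose | about 0 | about 0 |
| Error proportional to smallest adequate syringe | about 0 | at most 0.02 |

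Adjustment multiplies the standard error by roughly √(1 − R²): 0.99, 0.95 and 0.84 for R² of 0.02, 0.10 and 0.30.

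**5. Effect on the arm comparison.** Simulation with 70 per arm and 3,000 trials per setting. Assumed: mL error SD 0.30 in control and 0.20 in intervention, lognormal volume with median 2.5 mL, least squares with and without log volume. The figures are variance of the arm effect without adjustment divided by variance with it.

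| Setting | log-SD 0.4 | 0.6 | 0.8 |
|---|---|---|---|
| Constant mL error, log(1 + absolute percent error) | 1.18 | 1.38 | 1.67 |
| Constant mL error, over-20% indicator | 1.08 | 1.18 | 1.31 |
| Constant mL error, signed percent error | 1.00 | 1.02 | 1.03 |
| Error proportional to syringe capacity | 1.00 | 1.00 | 1.00 |

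With error proportional to dose the ratio is 0.99–1.00. A repeat run agreed with all of these to within simulation error.

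**6. Size of a chance imbalance.** With 72 per arm, the standard error of the difference in mean log volume is SD·√(2/72) = SD/6. For log-SDs of 0.4, 0.6 and 0.8, 1.96 standard errors are 0.131, 0.196 and 0.261. By chance alone, one trial in twenty would therefore have geometric mean volumes that differ between arms by a ratio of at least 1.14, 1.22 or 1.30.

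**The case against.** The strongest objection is that the gain depends on an error model that the documents do not supply. They give no SD of mL error, no distribution of volumes and no R². If syringes are matched to dose, as section 3.3 says for the intervention, error may scale with capacity and the gain disappears. This stands, and it is why the lower end of the range is 1.0. It is not decisive, because no size rule is given for the usual-care syringe.

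Secondly, the worked example in section 3.5 (a 50% overdose) suggests a signed outcome. On that scale a zero-centred error makes volume drive the spread and not the mean, so a covariate gains almost nothing. This also stands for the signed scale. The 20% outcome, which the plan commits to reporting, ignores sign.

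Thirdly, the adjusted analysis is contingent, so lengthening the list would not by itself change the primary result. That is correct, and the fix must therefore deal with the trigger as well.

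Fourthly, child age is listed and partly stands in for volume. It does so only in part: volume also depends on the drug and its concentration, and section 1.0 itself points to varying concentrations. Age is also not first-line.

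Two inferences should be resisted. A reader might conclude that an imbalance in volume could not even be noticed, but the baseline comparison in section 3.5 is not confined to the listed covariates, and nothing excludes dose from it. A reader might also take Table 4 (54% under 6 months) to show that small volumes will be common. The table covers all 1,742 discharges, of whom the plan says only that at least half went home on a medication, and it gives no volumes.

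**Conclusion.** The omission is a fact of the text: no covariate list in section 3.5 contains dose, volume, drug or concentration, while prescribed volume is the outcome's denominator and dose is in hand. The consequence is a possible loss of precision and an unhandled chance imbalance. The variance factor runs from about 1.0 to about 1.7 on the absolute scale, and from 1.0 to about 1.3 for the over-20% indicator. The upper ends need a constant mL error and widely spread volumes.

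The documents do not support saying that volume is a main source of outcome variance, because that rests wholly on the assumed error model. Nor do they support a statement about this trial's power. The simulated inputs give over-20% error rates of about 13–19% in control and 4–11% in intervention, against the plan's 30% and 10%. Randomisation means that the omission causes no bias, and the 72 per arm is unaffected. This is a worthwhile, low-cost improvement to the plan and not a flaw in its validity.

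**What to change.** In section 3.5:

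1. Add log(prescribed volume in mL of the study medicine) to the baseline comparison and to the first-line covariates.
2. Prespecify an adjusted analysis of absolute percent error and of the ±20% outcome that includes this term whether or not imbalance is detected. Report it beside the unadjusted comparison.
3. State whether the continuous outcome is signed or absolute, since that decides whether a covariate can help on that scale.

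Prior liquid-medicine use, already asked at enrolment, is an optional further covariate. No calculation here supports a gain from it.

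The cost is SAP wording and one model degree of freedom. No new data are needed, because prescribed mL is required to compute the outcome anyway. If volume proves unrelated to error, essentially nothing is lost (variance ratio 0.99–1.00).

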Specific Aim *In a randomized controlled trial, we will test the efficacy of a health literacy-informed communication intervention on caregiver discharge medication dosing accuracy, adherence, and comprehension. We hypothesize that a useable, health literacy-informed medication counseling intervention will be efficacious in reducing liquid medication dosing errors and improve adherence and medication comprehension among caregivers following hospital discharge for children receiving liquid medication as compared to usual care.*

The primary outcome is observed dosing accuracy assessed via picture of an oral dosing syringe submitted by a caregiver 48-72 hours following discharge and compared to the prescribed dose in the chart. The primary outcome will be a continuous measure of percent difference of the caregiver submitted photo compared to the prescribed dose (in mL). The primary measure will also be assessed as a dichotomous variable as +/- 20% from the prescribed dose. Secondary outcomes include caregiver medication adherence and medication comprehension assessed via caregiver follow-up survey.

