3.4 Assessment of Outcomes

Follow-up Survey via myCap: The follow-up survey will be completed 48 to 72 hours following discharge to assess study outcomes. This will be done via myCap. myCap is an application that research participants will be asked to download on their phones (application is free and available on iPhone and Android phones). myCap leverages REDCap to capture participant/patient reported outcomes via mobile devices. myCap is HIPPA-compliant and secure. All data collected via myCap converts results into a format compatible with REDCap. The primary outcome of dosing accuracy will be assessed along with secondary outcomes (medication adherence and medication comprehension) via surveys in myCap. Caregivers will also be asked who administered the medication, what kind of teaching they received in the hospital prior to discharged (i.e., did teach-back, show-back occur), whether any serious medication errors occurred with the patient or other children in the home and/or if there were unplanned visits to a health care provider (see included follow-up survey). Caregiver self-efficacy for administering medicines to their children will be assessed using a standardized scale called the Medication Understanding and Use Self-Efficacy Scale (MUSE). See included document for RCT follow-up survey. We anticipate that the caregiver follow-up survey this will take <15 minutes to complete.

Primary Outcome: Dosing accuracy will be the primary outcome and will be assessed through self-report (reported dose) and through observation (observed dose) at follow-up. The primary outcome will be *observed dosing accuracy*. For *observed dosing accuracy*, caregivers will be asked to draw up a dose of their child's medication using the provided oral dosing syringe and send a secure picture of the syringe via myCap to research study staff (see Figure 2 as an example). The primary outcome will be assessed as a continuous percent difference from the prescribed dose (in milliliters). For *reported dose*, caregivers will be asked to report the prescribed volume (in milliliters) of medication to be given with each dose during the follow-up myCap survey. This will be compared to the prescribed dose in the electronic medical record. For both measures, dosing accuracy will also be assessed as a dichotomous outcome and considered accurate if it is within 20% of the prescribed dose similar to prior studies.^{5,15}

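### The 80% power belongs to a 30% versus 10% dosing-error proportion; the declared continuous primary has no stated power, no unconditional between-arm test and no stated handling of sign

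*Combined protocol and SAP*

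**What the plan says.** The Specific Aim in section 2.0 states: "The primary outcome will be a continuous measure of percent difference of the caregiver submitted photo compared to the prescribed dose (in mL". Section 3.4 repeats it: "The primary outcome will be assessed as a continuous percent difference from the prescribed dose (in milliliters". Both sections add a dichotomous form, with a 20% margin either side of the prescribed dose.

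Section 3.5 defines the measure as observed minus prescribed dose, divided by prescribed dose. Its worked example, 4.5 mL against 3 mL, ends with "this would be a 50% overdosing error". The between-arm comparison is given as: "The observed dosing percent difference will be compared between the intervention and control groups as medians with interquartile ranges".

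Two other sentences in 3.5 name methods:
- "Wilcoxon rank-sum tests will be used if the data does not appear to be normally distributed" follows the comparison of baseline characteristics and is then extended to completers versus non-completers.
- "we will use propensity score weighting and a multivariable linear regression model to conduct an adjusted analysis" applies only if covariate imbalance is detected.

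For the 20% form, 3.5 plans relative and absolute risk reductions and number needed to treat with 95% confidence intervals. It introduces that form as an additional one that permits comparison with earlier literature.

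The Sample Size paragraph says "we will need to enroll 72 subjects in each arm of the study to reject the null hypothesis that the dosing error prevalence" is equal between arms, at 30% versus 10%, 80% power and two-sided 0.05. It does not say whether these rates refer to observed or reported dose.

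Table 3 lists only deviation above 20% under Primary Outcome, for reported as well as observed dose. Section 3.4 opens with "Dosing accuracy will be the primary outcome and will be assessed through self-report (reported dose) and through observation (observed dose) at follow-up" but then names observed accuracy as the primary.

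**The concern.** The power statement and the declared primary concern different quantities. A proportion beyond 20% and a continuous percent difference can respond very differently to the same intervention, so 80% power for one says nothing definite about the other.

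Three choices that determine the power of the continuous comparison are left open: whether the sign is kept, which test is used, and what spread is assumed among doses inside the 20% margin. If sign and test are not fixed in advance, the primary comparison can also be settled after the data are seen. The disagreement between Table 3 and the text leaves further room over which form, continuous or binary, observed or reported, is the headline result.

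**Working it through.** **1. Reproduce the plan's figure.** Inputs from 3.5: p1 = 0.30, p2 = 0.10, mean 0.20, two-sided alpha 0.05, power 0.80.

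n = [1.960·√(2·0.20·0.80) + 0.842·√(0.30·0.70 + 0.10·0.90)]² / 0.20² = (1.109 + 0.461)² / 0.04 = 61.6.

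With continuity correction: (61.6/4)·[1 + √(1 + 4/(61.6·0.20))]² = 71.2, rounded up to **72**. The figure reproduces. Fisher exact power at 72 per arm is 82.6%.

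**2. Look for the same inputs for the continuous primary.** None are given. For means, the detectable difference at 72 per arm is (1.960 + 0.842)·√(2/72) = 0.467 SD. Over assumed SDs of 10, 20, 30 and 40 percentage points that is 4.7, 9.3, 14.0 and 18.7 points. Without an SD and a target difference, no power follows.

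**3. What the stated summary would show at the plan's own rates.** If 30% and 10% of doses lie beyond the margin, 70% and 90% lie within it. Both population medians, signed or absolute, then fall inside the margin. If the within-margin doses are exact, both medians are zero despite a threefold fall in errors.

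**4. Power at 72 per arm when errors fall from 30% to 10%.** These assumptions are illustrative and not from the documents. Error size is 20 points plus an exponential with mean 20, with underdoses capped at 100%. Non-error doses are exact or normal truncated at ±20. Tests are two-sided at 0.05.

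| Measure | Non-error doses | Rank-sum | Welch |
|---|---|---|---|
| Signed, errors split evenly | any of those below | about 5% | about 5% |
| Signed, 75/25 split | equal spread to exact | 18% to 32% | 21% to 23% |
| Absolute | equal SD in both arms | about 55% | about 75% |
| Absolute | exact | 86% | 78% |
| Absolute | SD 5 control, 4 intervention | 86% | 82% |

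**5. Sensitivity to error size.** With errors instead uniform from 20% to 100% and three assumed shapes inside the margin:
- Signed, even split: about 5% to 6% by either test.
- Signed, all errors in one direction: 53% to 65% by rank-sum, 74% to 81% by Welch.
- Absolute deviation: 55% to 64% by rank-sum, 77% to 80% by Welch.

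**The case against.** The strongest reply is that the powered quantity is itself a prespecified form of the primary. Sections 2.0 and 3.4 say the measure will also be dichotomised, Table 3 defines the Primary Outcome row that way, and 3.5 plans risk reductions with 95% confidence intervals for it. This stands. A reader might infer that the powered form has no planned inference; the documents contradict that. It does not close the gap, because three sections name the continuous form as primary and 3.5 presents the 20% form as an addition.

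A second reply is that the low power figures depend on the chosen test. This also stands in part: on absolute deviation, Welch power is near 80% in most of these settings, and the 55% is specific to rank-sum. But the plan assigns neither test to the primary.

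A third is that a hypothesis about reducing dosing errors implies deviation from zero, and that one overdosing example cannot settle the sign. That is a reasonable guess at intent, but the formula as written takes no absolute value. With evenly split errors, a signed measure has about 5% power under either test.

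The rank-sum sentence may have been meant more broadly. Even so, it would settle neither the sign nor the power. Section 3.6 concedes that the powering assumptions may be inaccurate, but that concerns the size of the differences, not which outcome was powered.

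**Conclusion.** The mismatch is real and should be fixed. The sample size is correct for 30% versus 10% dosing error, and nothing here supports reading 72 as a miscalculation. A reader might also infer that the trial is underpowered for its primary. The documents do not support that: they give no distribution for the continuous measure, and its power may lie above or below 80%.

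Under the assumptions shown, 80% is roughly attainable with a mean-based test on absolute deviation (about 75% to 82%). It is not attainable with a signed measure unless errors run mostly in one direction. That the stated power is for a different quantity, that no unconditional test is named, and that the sign is unspecified all rest on the text alone. The power figures rest on assumed error sizes and non-error spread.

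**What to change.** In 3.5, state that the 80% applies only to the observed-dose proportion with error above 20%. Then choose one:

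- **(a)** Make that proportion the primary, analysed by the risk difference and 95% confidence interval already planned, and move the continuous measure to secondary.
- **(b)** Keep the continuous primary and define it as absolute percent deviation. Name one unconditional between-arm test or estimator with a 95% confidence interval, after comparing rank-sum and mean-based power. Keep medians and interquartile ranges as description, and report over- and underdosing separately. State simulated power at 72 per arm under stated assumptions, even if it is below 80%.

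Under either option, align Table 3 and the 3.5 sentence that treats observed and reported accuracy jointly as primary with section 3.4, so that observed dose is primary and reported dose secondary.

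Make the change by dated amendment, with the reason, before any aggregate comparison of outcomes by arm. A stricter condition may be unattainable, because enrolling staff know the allocation and the research team responds to individual dosing errors it detects.

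The cost is text edits to 2.0, 3.4, Table 3 and 3.5, plus a short simulation under (b). No participants are added. The downsides are a narrower power statement and an amendment to the primary during planned enrollment (12 months from July 1, 2021; last revision 4/21/2022). Option (a) loses detail in the primary; option (b) loses error direction from it.
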